### 9.2.4 Follow-up time

The cohort entry date (i.e. index date) is the date of LMP. This date is considered as the beginning of the pregnancy. The pregnancies are followed until induced abortion or birth. The births are followed-up for a maximum of 12 months for registration of MCAs (see section 9.2.3 Study period). Information on LMP, or gestational age, is not available for ectopic pregnancies or spontaneous abortions. The date of hospitalisation due to these outcomes will be used as a proxy of index date for these outcomes.

## 9.3 Data sources

### 9.3.1 Register data sources

All Nordic countries being studied (FIN, SWE, NOR) have well developed population-wide register systems with tens of years of longitudinal follow-up data. The persons are identified in the registers with a unique personal identification number (PIN) and thus the records can be linked for research purposes at the individual level between the various registers.

In the Nordic countries, births are covered by three different databases (Gissler 2010). First, all live births are registered to Central Population Registers, which are the basis for vital statistics. Second, all deaths of live born children are registered in Causes of Death Registers, maintained by statistical or health authorities. Third, all Nordic countries have introduced a separate MBR for more detailed collection of parturients, deliveries and newborns. Registers that could be used in the proposed pharmacoepidemiological study are described below in detail.

The present study will be based on data on births complemented with data obtained from Patient Registers, Prescription Registers and Population Registers. The following country-specific registers will be used: Reimbursement Register, Malformation Register (FIN), MBR (FIN, SWE, NOR), MS register (SWE, NOR) and Causes of Death Register (SWE) (Table 2).

**Table 2: List of relevant data sources in different countries.**

Finland		
Outcome	Register	Register holder
Ectopic pregnancies	Patient Register (Care Register for Health Care)	National Institute for Health and Welfare (THL)
Spontaneous abortions	Patient Register (Care Register for Health Care) (of previous pregnancies from DPP)	THL
Elective terminations	DPP	THL
Stillbirths with and without foetal defects	DPP	THL
Live births with and without congenital anomaly	DPP	THL

Exposure	DPP National Prescription Register National Reimbursement Register	THL Social Insurance Institution (SII)
MS population	DPP, Patient Register (Care Register for Health Care)	THL
General population	Population Register	Statistics Finland (SF)
Sweden		
Outcome	Register	Register holder
Ectopic pregnancies	Patient Register	National Board of Health and Welfare
Spontaneous abortions	Patient Register	National Board of Health and Welfare
Elective terminations	not recorded in SWE	N/A
Stillbirths with and without foetal defects	MBR	National Board of Health and Welfare
Live births with and without congenital anomaly	MBR	National Board of Health and Welfare
Exposure	Prescribed Drug Register	National Board of Health and Welfare
MS population	Patient Register, MS Register	National Board of Health and Welfare
General population	Population Register	Swedish Tax Agency
Norway		
Outcome	Register	Register holder
Ectopic pregnancies	Patient Register	Norwegian Directorate of Health
Spontaneous abortions	Patient Register (of previous pregnancies in MBR)	Norwegian Directorate of Health Norwegian Institute of Public Health (NIPH)
Elective terminations	MBR	NIPH
Stillbirths with and without foetal defects	MBR	NIPH
Live births with and without congenital anomaly	MBR	NIPH
Exposure	Prescription Register	NIPH
MS population	MS Register	Helse Bergen
General population	Population Register	Statistics Norway

### **9.3.1.1 MS diagnosis and Exposures**

#### **MS Registers (SWE, NOR)**

Information on MS diagnoses will be obtained from MS registers in SWE and NOR. The Norwegian MS Register was established in 1998 (Myhr et al. 2012). In 2012, the register included information on more than 5000 patients regarding demographics, diagnosis, disease modifying treatment and follow-up, as well as disease activity with clinical scoring and several patient-reported outcome measures. The register includes also information on patients' comorbidity, co-medication, and siblings with MS. During 2007 the registry was expanded to include a biobank for collection of blood samples (DNA and serum).

The Swedish MS Register was officially launched in 2001 and contains data since 1996. Since 2011 the register has been part of the Swedish Neuro Register. The register is a nationwide quality registry for patients diagnosed with MS. Most MS specialists in SWE use the Swedish MS Register to enter information on age at onset and sex as well as clinical parameters, such as disease course, relapses, and treatment. The register dates back to 2002 and contains mostly prospective cases, although some clinics have entered data retrospectively.

#### **Register on Reimbursed Medications (FIN)**

In FIN, information on chronic diseases can be obtained from the separate register on special medical reimbursements for treatment of chronic disease. Information on maternal MS diagnoses obtained from the DPP (FIN) is based on this Register on Reimbursed Medications maintained by the SII of Finland. All the patients who are entitled for special reimbursement due to MS diagnosis are included in the register. Reimbursement for MS requires a medical certificate demonstrating that the diagnosis is based on clinical examinations, fulfils international criteria, and is made by a board-certified physician. The medical certificate is issued when the MSDMD treatment is started.

#### **Prescription Registers (FIN, SWE, NOR)**

Information on maternal MSDMD exposure before and during pregnancy will be obtained from the Prescription Registers based on reimbursed drug purchases (information is linked to DPP in FIN). The Prescription Registers contain information on outpatient medication purchases in pharmacies (established FIN 1994, SWE 2005, NOR 2004). Prescription-only medicines are only sold in pharmacies, and dispensing requires a prescription issued by a physician or a dentist in FIN, SWE and NOR. In FIN, the register contains information on all purchased prescribed medicines that are reimbursed by the government. This excludes, for instance, most contraceptives. In SWE and NOR, all prescribed medicines purchased in community pharmacies are included irrespective of reimbursement status. The prescription data in the registers includes patient's ID, the generic name of the drug, ATC code, the brand name, the formulation and package, the amount as the defined daily dose (DDD), the date of purchase, the prescribing practice (primary vs. secondary healthcare), and the prescribing physician's area of specialisation.

### **9.3.1.2 Outcomes**

#### **Medical Birth Registers (FIN, SWE, NOR)**

Information on live births and stillbirths will be obtained from the MBR in each country (via DPP in FIN). Furthermore, information on abortions and MCAs will be obtained from MBR for NOR. The MBR's purpose for collecting data is to develop and organise maternity care, obstetrical services and neonatal care.

Each of the countries included in this study has kept medical birth registers for decades (established: FIN 1987, SWE 1973 and NOR 1967), with compulsory notification (Langhoff-Roos et al. 2014). All live births and stillbirths from varying gestational ages in the different countries are notified to the registers. There is some variation in content between the Nordic MBRs, but all the registers include some information on maternal socio-demographic background (e.g. marital status, age, smoking status), previous pregnancies and deliveries, maternal diagnoses (ICD-10 codes), care and interventions during pregnancy and delivery, and information on newborn health, diagnoses, care and interventions (Gissler 2010). Diagnoses are registered as ICD-8, ICD-9 and ICD-10 codes. The international origin of the codes for some main groups created through the registers allows for cross-country research on large populations within the Nordic countries. However, codes for each individual case are assigned nationally and this may involve minor differences between the countries. Birth notification forms are linked to MBRs and to population census offices.

The follow-up ends usually when the child is discharged from the hospital or, at the latest, until the end of perinatal period, i.e. the first week of living. Information on deaths, however, can cover the whole infant period until one year of age (Gissler 2010).

### **Malformation Register (FIN)**

Information on MCAs (FIN) will be obtained from the DPP, based on information from the Finnish Malformation Register. The Malformation Registers are usually closely linked to the MBR (FIN), or as a part of the MBR (NOR). Their follow-up period is usually from six to twelve months, and these registers also cover induced abortions due to foetal problems, except in SWE (Gissler 2010).

### **Register on Induced Abortions (FIN)**

In the Nordic countries, statistics on induced abortions are based on case data on an individual level (Gissler 2010). In SWE, however, the data collection is anonymous, and in NOR, the data collection is anonymous before 12 weeks of gestation. In FIN there is a separate Register on Induced Abortions and Sterilisations.

### **Patient Registers (FIN, SWE, NOR)**

Information on hospitalisations due to MS, spontaneous abortions, and ectopic pregnancies will be obtained from the Patient Registers in this study. The Patient Register includes individual-level inpatient data in FIN SWE and NOR (established: FIN 1969, SWE 1987, NOR 2008). Outpatient visits are available since 1998 in FIN, 2001 in SWE and 2008 in NOR. The registers include data on hospitalisations with information on diagnosis (ICD-10), start and end date of the hospitalisation period, operations and other procedures performed, and identification of the hospital and the hospital district. In addition, outpatient visits in the secondary healthcare units and day surgeries are included the registers. No primary care data are currently available.

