#### 9.2.3 Study period

The study periods in the different countries are as follows: FIN, 1 January 1996 – 31 December 2014; SWE, 1 July 2005 – 31 December 2014; NOR, 1 January 2004 – 31 December 2014. The start of the study period is determined by the availability of exposure data in each country. The end of the study period is determined by the availability of data on malformations. In FIN the follow-up period for the registration of MCA is 12 months after birth, in SWE 6 months. In NOR malformations are registered in the MBR and the newborns are followed until the end of the stay at the birth clinic (usually at least 4 days).

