cladribine	L01BB04	no	25.9.2000	19.11.1993	14.11.1996	injection no infusion yes
mitoxantrone	L01DB07	no	30.8.1993	29.10.1987	1.8.1988	yes
alemtuzumab	L01XC04	no	12.9.2013	no	no	yes
glatimer acetate (Copaxone ® )	L03AX13	yes	8.3.2004	21.9.2001	24.2.2004	no 
leflunomide	L04AA13	yes	2.9.1999	2.9.1999	5.11.2004	no
natalizumab	L04AA23	no	27.6.2006	27.6.2006	27.6.2006	yes
fingolimod	L04AA27	yes	17.3.2011	17.3.2011	17.3.2011	no
teriflunomide	L04AA31	yes	26.8.2013	26.8.2013	26.8.2013	no
azathioprine	L04AX01	yes	31.1.1968	14.3.1968	9.8.1968	no
dimethyl fumarate	N07XX09	no	30.1.2014	30.1.2014	30.1.2014	no

-  Information on only reimbursed medication can be acquired from the National Prescription Register in Finland.
-  Pre-filled syringes/pens and tablets.
-  Injection and infusion solutions - except Trexan injection solution, which is reimbursed.
-  Information on drug use in hospitals and outpatient clinics are not collected in the Prescription Registers and thus information on exposure to these types of medication is not available.
-  Some of the injections are given in hospital and some can be self-administered at home.
-  Earlier there may have been also products that have been administered in hospital.
-  Sources (accessed on 3.2.2015):  
[http://www.ema.europa.eu/ema/index.jsp?curl=pages/medicines/landing/epar\\_search.jsp&mid=WC0b01ac058001d124](http://www.ema.europa.eu/ema/index.jsp?curl=pages/medicines/landing/epar_search.jsp&mid=WC0b01ac058001d124),  
<http://www.fimea.fi/laaketieto/valmisteyhteenvetot/laakkeet>  
<http://www.lakemedelsverket.se/LMF>  
<http://www.legemiddelverket.no/Legemiddelsoek/>

**Outcome variables:** The primary (P), secondary (S) and exploratory (E) outcomes are presented here according to pregnancy timeline.

Ectopic pregnancies (S) (ICD-10: O00) and spontaneous abortions (S) (ICD-10:O03):

- Information will be obtained from Patient Register (FIN, SWE, NOR) based on hospital visits due to these diagnoses

Elective termination of pregnancy (P) (ICD-10: O04):

- Information will be obtained from the DPP (FIN) and from MBR (NOR), where the abortions are registered from GW 12.
- This information is not available from SWE.

Stillbirth (P):

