### 9.7.2 Denominators used for different pregnancy outcomes

The denominator used for the calculation of the descriptive statistics and prevalence of specific pregnancy outcomes in each study cohort varies by pregnancy outcome. Table 6 below describes how the denominators are defined for each pregnancy outcome.

**Table 6: Denominators used for calculation of the descriptive statistics and prevalence of pregnancy outcomes in each study cohort.**

Pregnancy outcome	Denominator used in each study cohort
Serious adverse pregnancy outcome	Number of elective terminations + number of births (still or live)
Elective TOPFA or other reasons	Number of elective terminations + number of births (still or live)
Still births	Number of elective terminations + number of births (still or live)
Live births	Number of elective terminations + number of births (still or live)
MCA	Number of elective terminations + number of births (still or live)
MCA in live births	Number of live births
Mode of delivery (CS/vaginal)	Number of live births, separately for single and multiple pregnancies
Preterm birth	Number of live births, separately for single and multiple pregnancies
Birth weight, LBW and birth weight, head circumference for gestational age	Number of live births, separately for single and multiple pregnancies
Sex of the newborn	Number of live births, separately for single and multiple pregnancies
Head circumference, low head circumference	Number of full-term live births, separately for single and multiple pregnancies
Apgar scores	Number of full-term live births, separately for single and multiple pregnancies
Ectopic pregnancies	Number of all pregnancy events
Spontaneous abortions	Number of all pregnancy events
Defect cases	Number of elective terminations + number of births (still or live)

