**Information on elective terminations, spontaneous abortions and stillbirths**

Information on elective TOPFA is not available from SWE, while in NOR information on pregnancy terminations is available only from GW 12 onwards. Furthermore, information on spontaneous abortions is incomplete in this study, as only women treated in hospitals due to spontaneous abortions are included in the data. Usually spontaneous abortions are in the early pregnancy and women may not even know yet about the pregnancy. Therefore estimates based on hospital records lead to underestimation of the actual number of spontaneous abortions. However, it is expected, but not certain, that the underestimation of spontaneous abortions would be comparable across cohorts. Therefore, any differences observed between cohorts are likely to be due to the differences in cohort exposure. As noted in section 9.7.2, the denominator for the prevalence of MCAs includes the number of elective terminations and the number of births (still or live). Because data on elective terminations are not available in SWE, the prevalence of MCAs will be calculated first in the data from FIN and NOR. The prevalence of MCAs will then be re-calculated to include MCAs identified from SWE. However, the denominator for this prevalence will exclude the elective TOPFAs identified from FIN and NOR.

Because information on elective pregnancy terminations is not available from SWE, analyses on MCAs will be calculated including TOPFA with Finnish and Norwegian data and for births without TOPFA including data from all three countries.

Information on pregnancy terminations is available from GW 12 onwards from the Norwegian data, and therefore, information on early pregnancy terminations conducted before GW 12 could result in incomplete data. Therefore we will conduct separate analyses by trimesters on pregnancy terminations.

Information on stillbirths is available from GW 28 onwards from the Swedish data. Country-specific prevalence rates will be estimated for outcomes, where stillbirths are included as nominator, or denominator.

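### Norwegian spontaneous abortions and ectopic pregnancies are sourced from a register that starts in 2008, but Norwegian births and terminations enter the denominator from 2004, so their prevalence is understated

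*Protocol*

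**What the plan says.** Protocol section 9.4 gives the outcome source for ectopic pregnancies and spontaneous abortions: "Information will be obtained from Patient Register (FIN, SWE, NOR) based on hospital visits due to these diagnoses". Table 2 names the same register for both outcomes in Norway. For spontaneous abortion only, it adds the Medical Birth Register (MBR) as a record of previous pregnancies.

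Section 9.3.1.2 dates the Patient Registers: "The Patient Register includes individual-level inpatient data in FIN SWE and NOR (established: FIN 1969, SWE 1987, NOR 2008". It adds: "Outpatient visits are available since 1998 in FIN, 2001 in SWE and 2008 in NOR". Norway therefore has neither inpatient nor outpatient data from this source before 2008.

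Section 9.2.3 sets the Norwegian period as "NOR, 1 January 2004 – 31 December 2014" and gives the reason: "The start of the study period is determined by the availability of exposure data in each country". Table 6 in section 9.7.2 sets the denominator for both outcomes as "Number of all pregnancy events". Section 9.7.1 includes every pregnancy event in the study period. None of these places gives a later Norwegian start for these two outcomes.

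**The concern.** The protocol fixes the outcome source, the calendar period and the denominator, and for Norway in 2004-2007 the three do not fit together. Births and terminations from 12 gestational weeks reach the dataset through the MBR from 2004. Pregnancies that ended in a hospital-treated spontaneous abortion or an ectopic pregnancy in those years do not reach it through the Patient Register. They are absent altogether, so the proportion of pregnancies ending in loss comes out too low.

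This matters because the background prevalence of adverse outcomes in women with MS unexposed to IFN-beta is what the CHMP asked for (section 8), and spontaneous abortion is the possible risk that section 7 weighs against stopping treatment. Objective 7 is also affected. Expected counts for cohort 3 are matched on age and country, so Norwegian pregnancies from 2004-2007 would add expected events that the named source could not have recorded.

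The comparisons between cohorts could be distorted as well, if exposed and unexposed pregnancies fall differently across the two periods. Main effects for country and year do not represent a deficit that applies to Norway before 2008 only.

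**Working it through.** **Inputs**
- Norwegian births 2004-2014: 330; non-birth share: 0.2 (section 9.5 and the notes to Table 5).
- Total MS pregnancies: 1671 = 777 (Finland) + 482 (Sweden) + 412 (Norway) (section 9.5).
- Share exposed to IFN-beta: 22% (section 9.5).
- Norwegian Patient Register start: 2008 (section 9.3.1.2).
- Assumptions: Norwegian pregnancies are spread evenly over the years; the 20% non-birth share stands in for the prevalence of recorded losses.

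**The plan's own figure.** 330/0.8 = 412.5 (stated as 412), and 777 + 482 + 412 = 1671. Both reproduce. Norwegian non-births: 412 - 330 = 82.

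**The gap.** 2004-2007 is 4 of 11 years, or 36.4%.
- Births in the gap: 330 × 4/11 = 120.
- Losses not observable: 82 × 4/11 = 29.8, about 30.
- Losses observable: 82 × 7/11 = 52.2, about 52.

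**Norwegian prevalence.** Observed: 52.2/(330 + 52.2) = 13.7%, against about 20%. That is about 31% lower in relative terms. With numerator and denominator both limited to 2008-2014: 52.2/(210 + 52.2) = 19.9%, which restores the 20%.

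**Pooled prevalence, with the same true prevalence p in all three countries.** Losses missing: L = 412 × 4/11 × p. Observed: (1671p - L)/(1671 - L).
- p = 20%: L = 30.0; 304.2/1641.0 = 18.5%, about 7% lower in relative terms.
- p = 5%: L = 7.5; 76.1/1663.5 = 4.6%, about 9% lower.

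**Pooled relative risk, true RR = 1, p = 20%.** Norwegian pregnancies: 149.8 in 2004-2007 and 262.2 in 2008-2014; Finland plus Sweden: 1259, with a 22% exposed share. The Norwegian exposed shares are illustrative; the protocol gives none by period.
- Share rising from 15% to 25%. Exposed: 0.2 × (65.5 + 277.0) = 68.5 events over 149.8 × 0.15 × 0.8 + 342.5 = 360.5, or 19.0%. Unexposed: 235.7/1280.5 = 18.4%. RR = 1.03.
- Share falling from 25% to 15%. Exposed: 63.3/346.3 = 18.3%. Unexposed: 241.0/1294.8 = 18.6%. RR = 0.98.
- At p = 5% the same two cases give 1.04 and 0.98.

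If exposed and unexposed pregnancies divide between the two periods in the same proportions within Norway, the Norwegian RR is 1.00.

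**The case against.** Several points stand.
- These are secondary and exploratory outcomes. The primary composite and its components are divided by terminations plus births (Table 6) and are untouched.
- Section 9.7 pools the three countries. The Norwegian data alone would give crude RRs of 1.19 and 0.80 under the same illustrative shares, and a reader might take those as the bias in the study's comparisons. They are not: the planned comparisons are pooled, and there the figures shrink to 1.03 and 0.98.
- A reader might infer that no Norwegian event before 2008 could be recorded at all. For spontaneous abortion Table 2 does not support that, because it lists the MBR record of previous pregnancies. That source is partial: it needs a later registered pregnancy, and section 9.2.4 indexes these outcomes on the hospitalisation date. For ectopic pregnancy no second source is listed.
- Counting the 2004-2007 births and terminations as pregnancies without these outcomes is correct in itself. The error lies in the missing losses beside them.

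Other points do not dispose of the matter.
- Objective 4 is made subject to data availability by country, but the reason given is that only hospital-treated cases are seen. This would permit a year limit and does not set one.
- Section 9.9 admits under-recording and says "it is expected, but not certain, that the underestimation of spontaneous abortions would be comparable across cohorts". That discussion concerns losses not treated in hospital and does not mention the 2008 start.
- The 2005-2014 sensitivity analysis in section 9.7.6 serves the primary objective and still contains 2005-2007.
- A statistical analysis plan could add a calendar window, but the protocol has already fixed a source, period and denominator that conflict.

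**Conclusion.** The point holds for spontaneous abortions and ectopic pregnancies. Followed as written, the plan understates their prevalence: by about 31% in relative terms in Norway (13.7% against 20%) and by about 7% in the pooled data (18.5% against 20%), rising to about 9% if the true prevalence is nearer 5%. These sizes rest on an even spread over years and equal prevalence across countries. They also rest on the protocol's 0.2, which is a planning share of non-births and not a measured hospital-recorded prevalence. The direction of the prevalence bias needs no assumption about exposure.

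Bias in the RRs is conditional on a change in IFN-beta use between the two Norwegian periods, and is small in the pooled comparison under the shares tried.

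A reader might see the same defect in Finland, whose period opens in 1996 with outpatient visits available only from 1998. The protocol does not support that: Finnish inpatient data go back to 1969, so 1996-1997 is thinner but not empty.

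**What to change.** For spontaneous abortions and ectopic pregnancies in objectives 4 and 7, limit the Norwegian numerator, denominator and expected counts to pregnancy events from 1 January 2008. State this in section 9.2.3 and as a footnote to Table 6, and describe the gap in section 9.9. Keep the 2004 start for outcomes taken from the Norwegian MBR. For Finland, note only that 1996-1997 is inpatient-only for these outcomes.

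The cost is a sentence, a footnote and a limitation. On the even-spread assumption, about 120 Norwegian births from 2004-2007, and any terminations recorded in those years, leave these two analyses. They carry almost no information on these outcomes.
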